2.8.4 Other safety data

Data from other tests (e.g., electrocardiogram) will be summarized and listed, notable values will be flagged, and any other information collected will be listed as appropriate.

All assessments collected later than 30 days after the last treatment/exposure date will be flagged in the listings.

Any statistical tests performed to explore the data will be used only to identify any interesting comparisons that may warrant further consideration.

2.8.4.1 Vital signs

Vital sign assessments will be performed in order to characterize basic body function. The parameters expected to be collected include height (cm), weight (kg), body temperature (°C), pulse rate (beats per minute), systolic and diastolic blood pressure (mmHg).

The criteria for clinically notable abnormalities are defined as follows:

Clinically notable elevated values

- systolic BP: ≥ 180 mmHg and an increase ≥ 20 mmHg from baseline
- diastolic BP: ≥ 105 mmHg and an increase ≥ 15 mmHg from baseline
- body temperature: $\geq 39.1^{\circ}\text{C}$

- weight: increase from baseline of $\geq 10\%$
- pulse rate: ≥ 120 bpm with increase from baseline ≥ 15 bpm

Clinically notable below normal values

- systolic BP: ≤ 90 mmHg and a decrease ≥ 20 mmHg from baseline
- diastolic BP: ≤ 50 mmHg and a decrease ≥ 15 mmHg from baseline
- body temperature: $\leq 35^{\circ}\text{C}$
- weight: decrease from baseline of $\geq 10\%$
- pulse rate: ≤ 50 bpm with decrease from baseline ≥ 15 bpm.

The following summaries will be produced for each vital sign parameter:

- summary statistics for change from baseline to the worst post-baseline value (in both directions, i.e., from baseline to the highest post-baseline and from baseline to the lowest post-baseline value)
- number and percentage of subjects with at least one post-baseline vital sign abnormality (in both directions, i.e., both elevated and below normal values).

In addition, the following two listings will be produced by treatment group:

- subjects with clinically notable vital sign abnormalities
- all vital sign assessments will be listed by subject and vital sign parameter.

In both listings, the clinically notable values will be flagged and also the assessments collected later than 30 days after the last treatment/exposure date will be flagged.

2.9 Interim analysis

Not applicable.

3 Sample size calculation

Refer to CRAD001Y2202 SAP Addendum 1 for details.

4 Change to protocol specified analyses

No change from protocol specified analysis was made.

5 Appendix

5.1 Baseline comparability

Appropriate descriptive statistics of baseline variables will be provided as in-text tables in the core CSR and also in Section 14 in the post-text tables. The summaries will be presented by treatment group, but no p-values will be provided.

5.2 Time-to-event analyses

The following sections present a general methodology to be used to analyze the following time-to-event variables:

- Progression-free survival
- Overall survival
- Time to definitive deterioration in the ECOG score by one category of the score from baseline

5.2.1 Analysis of time to event data with ties

The STRATA statement in the SAS LIFETEST procedure will be used to analyze time-to-event data with ties. The SAS PHREG procedure with option TIES=EXACT will be used to fit the Cox proportional hazards model.

5.2.2 Kaplan-Meier survival function estimation

The survival function in each treatment group will be estimated using the Kaplan-Meier (product-limit) method as implemented in PROC LIFETEST (see Figure 4-2 below). In each treatment group, the estimated median PFS time, along with the approximate 90% confidence interval, will be obtained from the PROC LIFETEST output. The log-log transformation option available within PROC LIFETEST will be used to compute the confidence intervals. The Kaplan-Meier graphs will be obtained from the SAS software. The hazard ratio point and interval estimates will be displayed in the figures.

5.2.3 Hazard ratio estimation

The hazard ratio as a measure of treatment effect will be derived from the **Cox proportional hazards model** using SAS procedure PHREG with TIES=EXACT option in the MODEL statement. The **stratified unadjusted Cox model** will be used (where the baseline hazard function is allowed to vary across strata) for the primary and secondary analyses, i.e., the MODEL statement will include the indicator of assignment to the everolimus + exemestane arm as the only covariate, and the STRATA statement will include the stratification variable obtained through IRT.

The two-sided 90% asymptotic confidence interval for the hazard ratio will be based on **the Wald test**.

5.3 Median follow-up of the study

Median study follow-up (in months) in this study will be calculated as

([analysis cut-off date] - [median randomization date] + 1)/30.4375, where 30.4375 is the average duration of a month in days: $365.25/12 \approx 30.4375$.

The median randomization date is obtained by first sorting all subjects in the FAS by the randomization dates, respectively, and then taking the date of the median subject (i.e., the subject in the middle of the sorted list in case of an odd number of subjects or the average between the two subjects in the middle of the sorted list in case of an even number of subjects).

The time from last contact date to data cut-off date will be summarized by time intervals in increments of 6 weeks.

The number of subjects at risk of death and the number of deaths in intervals of time with increments of 6 weeks will be summarized during the course of the trial using the life table method. The Kaplan-Meier estimates of survival probabilities and associated standard errors will be provided.

5.4 Imputation rules

5.4.1 Study drug

The following rule should be used for the imputation of date of the last administration for a given study treatment component:

Scenario 1: If the date of last administration is completely missing and there is no EOT page and no death date, the subject is considered as on-going:

The subject should be treated as on-going and the cut-off date should be used as the dose end date. The scenario is only used for interim analysis.

Scenario 2: If the date of last administration is completely or partially missing and the EOT page is available:

Case 1: The date of last administration is completely missing, and the EOT completion date is complete, then this latter date should be used.

Case 2: Only Year(yyyy) of the date of last administration is available and yyyy < the year of EOT date:

Use Dec31yyyy

Case 3: Only Year(yyyy) of the date of last administration is available and yyyy = the year of EOT date:

Use EOT date

Case 4: Both Year(yyyy) and Month (mm) are available for the date of last administration, and yyyy = the year of EOT date and mm < the month of EOT date:

Use last day of the Month (mm)

Case 5: Both Year (yyyy) and Month(mm) are available for the date of last administration, and yyyy = the year of EOT and mm = the month of EOT date, use EOT date if day of EOT not missing or use the first day of month if date of EOT missing.

All other cases should be considered as a data issue and the statistician should contact the data manager of the study.

After imputation, compare the imputed date with start date of treatment, if the imputed date is < start date of treatment:

Use the treatment start date

Subjects with missing start dates are to be considered missing for all study treatment component related calculations and no imputation will be made. If start date is missing then end-date should not be imputed.

5.4.2 AE date imputation

No imputation of missing or incomplete data will occur except for AE start dates in the determination of treatment emergence as described below:

If the date is completely missing, then it will be set to the first dose date.

If the day is missing, then the first day of the month will be used. If this date is before the first dose date and the months are the same, then the first dose date will be used.

If the day and month are missing, then the first day of the year will be used. If this date is before the first dose date and the years are the same, then the first dose date will be used.

If the imputed AE onset date is after the AE stop date, then the AE stop date will be used.

The original partial or missing dates rather than the imputed dates will be presented in data listings. Missing AE start times will not be imputed.

5.4.3 Concomitant medication date imputation

5.4.3.1 Prior therapies date imputation

For prior or concomitant medications, including rescue medications, incomplete (ie, partially missing) start dates and/or stop dates will be imputed. When the start date and stop date are both missing start dates and/or stop dates will be imputed. When the start date and stop date are both incomplete for a subject, impute the start date first.

Incomplete Start Dates

If the field of year is missing, then no value will be imputed. The following rules will be applied to impute the incomplete start date, assuming year is available. If the stop date is complete and the imputed start date is after the stop date, then the start date will be imputed using the stop date.

Missing Day and Month

If the year of the incomplete start date is the same as the year of the date of the first dose of study treatment, then the day and month of the date of the first dose of study treatment will be assigned to the missing fields.

If the year of the incomplete start date is before the year of the date of the first dose of study treatment, then December 31 will be assigned to the missing fields.

If the year of the incomplete start date is after the year of the date of the first dose of study treatment, then January 1 will be assigned to the missing fields.

Missing Month Only

The day will remain the same as observed and the month will be replaced according to the procedure in the preceding subsection.

Missing Day Only

If the month and year of the incomplete start date are the same as the month and year of the date of the first dose of study treatment, then the day of the date of the first dose of study treatment will be assigned to the missing day.

If either the year is before the year of the date of the first dose of study treatment or if both years are the same but the month is before the month of the date of the first dose of study treatment, then the last day of the month will be assigned to the missing day.

If either the year is after the year of the date of the first dose of study treatment or if both years are the same but the month is after the month of the date of the first dose of study treatment, then the first day of the month will be assigned to the missing day.

Incomplete Stop Dates

If the field of year is missing, then no value will be imputed. The following rules will be applied to impute the missing numerical fields, assuming year is available. If the date of the last dose of study treatment is missing, then replace it with the last visit date. If the imputed stop date is before the start date (imputed or non-imputed start date), then the stop date will be imputed using the start date.

Missing Day and Month

If the year of the incomplete stop date is the same as the year of the date of the last dose of study treatment, then the day and month of the date of the last dose of study treatment will be assigned to the missing fields.

If the year of the incomplete stop date is before the year of the date of the last dose of study treatment, then December 31 will be assigned to the missing fields.

If the year of the incomplete stop date is after the year of the date of the last dose of study treatment, then January 1 will be assigned to the missing fields.

Missing Month Only

The day will be the same as observed and the month will be replaced according to the procedure in the preceding subsection.

Missing Day Only

If the month and year of the incomplete stop date are the same as the month and year of the date of the last dose of study treatment, then the day of the date of the last dose of study treatment will be assigned to the missing day.

If either the year is before the year of the date of the last dose of study treatment or if both years are the same but the month is before the month of the date of the last dose of study treatment, then the last day of the month will be assigned to the missing day.

If either the year is after the year of the date of the last dose of study treatment or if both years are the same but the month is after the month of the date of the last dose of study treatment, then the first day of the month will be assigned to the missing day.

5.4.3.2 Post therapies date imputation

The date imputation method will be similar to the above section.

5.4.4 Death date imputation

If the day is missing, then a) if the year and month of EOT is the same as year and month of death, then use the EOT date; b) if the year of death is later than year of EOT, then use the first day of the first month in this year; c) if the year of the death is the same as year of EOT and month is later than month of EOT, then use the first day of the month. If the month and day are missing, then a) if the year of EOT is the same as year of death, then use the EOT date; b) if the year of death is later than the year of EOT, then use the first day of the first month in this year (JAN01).

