##### **14.1.4.1 Study/project specific decisions**

For each study (or project) various issues need to be addressed and specified in the protocol or RAP documentation. Any deviations from protocol must be discussed and defined at the latest in the RAP documentation.

The proposed primary analysis and potential sensitivity analyses should be discussed and agreed with the health authorities and documented in the protocol (or at the latest in the RAP documentation before database lock).

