##### **14.1.4.5.3 Incomplete dates for last known date patient alive or death**

All dates must be completed with day, month and year. If the day is missing, the 15th of the month will be used for incomplete death dates or dates of last contact.

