2.7.3 Handling of missing values/censoring/discontinuations

The same statistical principles will be applied, and supportive analyses conducted as described in [Section 2.5.3](#) for the handling of missing values/censoring/discontinuations.

The partial missing death date will be imputed following the rules in Section 5.4.4, but the complete missing death date won't be imputed. For the purpose of analysis, the patient with a complete missing death date will be censored at the last contact date.

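### SAP 5.4.4 throws away a recorded month of death: a day-missing death in a calendar year after end of treatment is set to 1 January, against the protocol's 15th of the month, and SAP section 4 declares no change

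*SAP*

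**What the plan says.** SAP 5.4.4 has two rules: one for a missing day, one for month and day both missing.

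The day-missing rule has three branches:

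- Branch (a), death in the same month and year as EOT: the death is dated to EOT.
- Branch (b), death in a later calendar year: "if the year of death is later than year of EOT, then use the first day of the first month in this year".
- Branch (c), death in the same calendar year, but "month is later than month of EOT, then use the first day of the month".

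The month-and-day-missing rule repeats the wording of (b) for a later year and glosses it as JAN01.

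SAP 2.7.3 puts these rules to use: "The partial missing death date will be imputed following the rules in Section 5.4.4". A completely missing death date is not imputed; that patient is censored at last contact.

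Protocol Appendix 1, 14.1.4.5.3 has one rule for a missing day: the 15th "of the month will be used for incomplete death dates or dates of last contact". Section 14.1.4.1 of the same appendix adds: "Any deviations from protocol must be discussed and defined at the latest in the RAP documentation". SAP section 4 states: "No change from protocol specified analysis was made".

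**The concern.** Branches (a) and (c) compare the month of death with the month of EOT, and a separate rule covers an unknown month. In the day-missing rule the month is therefore recorded. Branch (b) discards it and gives the same answer as if it were unknown. It looks like a phrase carried over from the other rule.

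The error has one direction: affected deaths are dated too early, so OS is shortened. SAP 2.7 plans a single OS analysis, at the end of the study. The imputed date always falls after EOT, because its year is later, but nothing keeps it after later survival contacts. The analysis data could then show patients alive after their imputed death. Deaths that enter the ECOG-deterioration analysis could be misdated in the same way.

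**Working it through.** **1. Is there another reading?** The neighbouring rules point one way.

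| Place | Situation | Recorded month kept? |
|---|---|---|
| SAP 5.4.4, day missing, (c) | same year as EOT, later month | yes, 1st of month |
| SAP 5.4.3.1, stop date, day only missing | year after last dose | yes: "then the first day of the month will be assigned to the missing day" |
| SAP 5.4.2, AE start, day missing | general | yes, 1st of month |
| Protocol 14.1.4.5.3 | death, day missing | yes, 15th of month |
| **SAP 5.4.4, day missing, (b)** | **year after EOT** | **no, 1 January** |

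**2. Size of the shift per death.** Shift = (15th of recorded month) − (1 January). For January to December of a non-leap year: 14, 45, 73, 104, 134, 165, 195, 226, 257, 287, 318, 348 days. The sum is 2,166, and 2,166/12 = 180.5 days, or 180.5/30.4375 = 5.9 months if deaths are spread evenly over months. In a leap year December gives 349. Against the true date, the SAP rule is 0 to 364 days too early (mean 182, non-leap year); the protocol rule is within −14 to +16 days (mean 0.7).

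**3. Illustrations (assumed dates).**

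- Randomized 1 March 2019, EOT 10 November 2019, last contact 20 September 2020, death October 2020 with day missing. SAP rule: OS 307 days (10.1 months). Protocol rule: 595 days (19.6 months). The patient was known alive at day 570.
- Death November 2020 with day missing. EOT on 5 January 2020 leads to branch (c), 1 November 2020. EOT on 31 December 2019 leads to branch (b), 1 January 2020. A five-day difference in EOT moves the death by 305 days.

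**4. Conflict with survival contacts.** Protocol Table 7-1 schedules survival follow-up every 12 weeks (84 days). From 1 January to 1 April is 90 days, so any affected death from April onward has at least one scheduled contact between its imputed and true dates.

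**5. Effect on OS.** The documents do not give the number of day-missing deaths, so this step is conditional on assumed rates. Simulation inputs:

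- 400,000 patients per arm; uniform accrual over 18 months (Protocol 10.6) from July 2017 (Amendment 1).
- Cut-off assumed at 9 February 2022, the approval date in SAP section 1.
- EOT taken as the PFS time, medians 4.1 and 6.6 months (Protocol 10.6).
- OS medians 26.55 and 30.98 months, control and everolimus (Protocol 1.1.2).
- Model A: OS = PFS plus an exponential remainder, medians 20.10 and 20.56 months, solved to match the OS medians. Model B: exponential OS independent of progression, with PFS the earlier of the two.

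| | Model A | Model B |
|---|---|---|
| Dead by cut-off, control / everolimus | 74% / 69% | 70% / 64% |
| Deaths per 160 patients | about 115 | about 107 |
| Share of deaths in a year after EOT (pooled) | 75% | 61% |
| Mean shift of affected deaths v the 15th, days | 165.8 | 168.6 |
| Imputed date before last scheduled contact | 84.4% | 84.8% |

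Deaths exposed to branch (b): 115 × 0.75 ≈ 86 (A) and 107 × 0.61 ≈ 65 (B). At 5%, 10% and 20% day-missing, that is about 3–4, 7–9 and 13–17 affected deaths.

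| Day missing (both arms) | Median OS, A (control / everolimus) | HR, A | Median OS, B (control / everolimus) | HR, B |
|---|---|---|---|---|
| 0% | 26.61 / 31.08 | 0.8345 | 26.58 / 30.95 | 0.8572 |
| 5% | 26.35 / 30.78 | 0.8344 | 26.32 / 30.69 | 0.8567 |
| 10% | 26.12 / 30.49 | 0.8342 | 26.09 / 30.42 | 0.8558 |
| 20% | 25.63 / 29.90 | 0.8333 | 25.63 / 29.86 | 0.8549 |

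The medians fall by 0.26–0.30, 0.49–0.59 and 0.95–1.18 months. The 15th-of-month rule moves them by 0.03 month or less. The HR changes by at most 0.0023. If 10% are missing in one arm only, it becomes 0.824 (control) or 0.845 (everolimus) in A and 0.850 or 0.863 in B: a change of 0.006–0.010.

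For scale, with 80 × 0.74 ≈ 59 control deaths, an approximate 90% CI for the control median is 26.6 × exp(±1.645/√59) = 21.5 to 33.0 months.

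**The case against.** The wording defect is hard to dispute; the argument is about how much it matters.

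*The protocol rule is not binding.* Protocol 14.1.4 calls itself guidance, and 14.1.4.1 asks only that deviations be discussed and defined in the analysis documentation. SAP 5.4.4 is such documentation and sets out its rule in full. This stands in part: a different rule is allowed. But SAP section 4 tells the reader there is no change, and permission to deviate does not justify dropping a recorded month.

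*Incidence may be nil.* The protocol requires complete dates and missing values are queried, and the 5–20% rates have no source in the documents. This stands; at 0% nothing changes.

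*The consequence is small.* At 5%, the shift in the median is under 3% of the width of the control median's interval; at 20%, about a tenth. The HR barely moves. OS is secondary with no test, the primary report used a May 2020 cut-off, and the indication was approved in February 2022. All of this stands and limits the severity.

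*The simulation is rough.* It combines PFS assumptions based on Asian patients with OS medians from the whole phase III population, gives an OS HR of 0.83–0.86 against the 0.89 cited in the protocol, equates EOT with progression, ignores loss to follow-up, and counts scheduled rather than recorded contacts. This stands too; the OS shifts are orders of magnitude. The 14 to 348 day shift per death needs no model.

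**Conclusion.** The concern holds. Followed exactly, branch (b) ignores a recorded month and backdates an affected death by 14 to 348 days (349 in a leap year) relative to the protocol's rule. The separate rule for an unknown month, its JAN01 gloss, branch (c) and the medication rules leave no benign reading. The departure from the protocol is undeclared.

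The effect on reported OS depends on an unknown count. Under the assumed 5–20% rates, median OS in each arm is understated by roughly 0.3 to 1.2 months and the HR is essentially unchanged unless missing days differ between arms. It should be fixed because the rule is wrong as written and the bias has one direction. It does not bear on the primary PFS conclusion already reported.

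**What to change.** - In the day-missing rule, branch (b), keep the recorded month and use the 15th, as in Protocol 14.1.4.5.3. Reserve JAN01 for dates with month and day both missing.
- As an addition that the protocol does not contain, set any imputed death date no earlier than the day after the last date the patient was known alive.
- State in SAP section 4 whatever still differs from 14.1.4.5.3, including branches (a) and (c), which use the EOT date and the 1st of the month.
- Report the number of imputed death dates by arm, so that readers can see whether the rule mattered.

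Cost: one line of SAP wording, a sentence in section 4 and a few lines of code. No new data are needed.

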##### **14.1.4.2 End of treatment phase completion**

Patients may voluntarily withdraw from the study treatment or may be taken off the study treatment at the discretion of the investigator at any time. For patients who are lost to follow-up, the investigator or designee should show "due diligence" by documenting in the source documents steps taken to contact the patient, e.g., dates of telephone calls, registered letters, etc.

The end of treatment visit and its associated assessments should occur within 7 days of the last study treatment.

Patients may discontinue study treatment for any of the following reasons:

- Adverse event(s)
- Lost to follow-up
- Physician decision
- Pregnancy
- Protocol deviation
- Technical problems
- Subject/guardian decision
- Progressive disease
- Study terminated by the sponsor
- Non-compliant with study treatment
- No longer requires treatment
- Treatment duration completed as per protocol (optional, to be used if only a fixed number of cycles is given)

Death is a reason which “**must**” lead to discontinuation of patient from trial.

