2.1.8 On-treatment assessment/event

On-treatment assessment/event is defined as any assessment/event obtained in the time interval:[date of first administration of study treatment; date of last administration of study treatment + 30 days], i.e., including the lower and upper limits. (Note: The calculation of study treatment duration, however, may use different rules as specified in [Section 2.4.1](#).)

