2.1.9 Last contact date

The last contact date will be derived for subjects not known to have died at the final analysis cut-off using the sources presented in [Table 2-1](#) below:

Table 2-1 Last contact date data sources

Source data	Condition
Last contact date/last date subject was known to be alive from survival follow-up page	Subject status is reported to be alive. Do not use if subject status is reported unknown.
Start/End dates from further antineoplastic therapy	Non-missing medication/procedure term.
Start/End dates from drug administration record	Non-missing dose. Doses of 0 are allowed.
End of treatment date from end of treatment page	No condition.
Tumor (RECIST) assessment date	Evaluation is marked as ‘done’.
Laboratory collection dates	Sample collection marked as done.
Vital signs date	At least one non-missing parameter value.
Performance status date	Non-missing performance status.
Start/End dates of AE	Non-missing verbatim term.

The last contact date on or before the data cut-off date should be used; the cut-off date should not be used as the censoring date (even in presence of post cut-off data) unless the subject was seen or contacted on the cut-off date.

Imputed dates (e.g., analysis cut-off date programmatically imputed to replace the missing end date of a dose administration record) will not be used to derive the last contact date. Partially imputed dates (i.e., only day or day and month imputed) are allowed to be used for last contact date only if coming from Survival Follow-up page.

The last contact date will be used for censoring of subjects in the analysis of overall survival.

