2.8.2 Deaths

The number of deaths resulting from SAEs suspected to be related to study treatment and SAEs irrespective of study treatment relationship will be provided by SOC and PT. Summaries of all deaths and on-treatment deaths will be provided.

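### A death known only by year is dated at the EOT visit (or 1 January) with no check against later evidence of life, so the imputed death can precede a recorded alive contact

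*SAP*

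**What the plan says.** SAP 5.4.4 imputes partial death dates. If day and month are both missing and death fell in the calendar year of EOT, the instruction is: "if the year of EOT is the same as year of death, then use the EOT date". If the year of death is later, the date is 1 January of that year. If only the day is missing, the date is the EOT date (same month and year as EOT), 1 January (later year) or the first of the month (later month in the EOT year).

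SAP 2.7.3, under secondary efficacy, calls this rule: "The partial missing death date will be imputed following the rules in Section 5.4.4". It adds that a completely missing death date is not imputed and that the patient is censored at last contact.

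SAP 2.1.9 limits the derivation of last contact: "The last contact date will be derived for subjects not known to have died at the final analysis cut-off".

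SAP 2.1.8 runs the on-treatment interval from first dose to "date of last administration of study treatment + 30 days". SAP 2.8.2 states: "Summaries of all deaths and on-treatment deaths will be provided". The timing of EOT is in Protocol 14.1.4.2: "The end of treatment visit and its associated assessments should occur within 7 days of the last study treatment".

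Protocol 14.1.4.5.3 asks for complete dates and uses the 15th of the month when the day of death is missing. It has no year-only rule. SAP section 4 declares no change from the protocol's analyses.

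**The concern.** No branch of 5.4.4 compares the imputed death with the last date the patient was known alive, and no other section supplies that comparison. Other imputed dates do get a check: last dose against treatment start (5.4.1), AE onset against AE stop (5.4.2) and medication stop against start (5.4.3).

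Alive contacts after EOT are expected. Protocol 7.1.6.3 requires survival status at least every 3 months, and 7.1.6.2 continues scans in patients who stop treatment without progression. A death placed at EOT can therefore sit before dated records of the living patient.

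What is at stake:
- OS times that the patient's own record contradicts.
- Possibly, extra entries in the on-treatment death summary, where single cases are visible.
- Possibly, a PFS or ECOG-deterioration event at EOT in a patient with no earlier event, since death can count as an event in both.

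**Working it through.** The plan gives no figure for this rule, so there is none to reproduce. I applied the rule to illustrative dates, then sized it under stated assumptions.

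**1. Same-year case.** EOT 10 Feb 2020; survival contact, alive, 20 Oct 2020; death recorded as 2020.
- Imputed death: 10 Feb 2020.
- 10 Feb to 20 Oct 2020 = 253 days, so OS is at least 253 days too short.
- The largest possible shift in a 365-day year is 1 January to 31 December = 364 days.

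**2. Later-year case.** EOT in November 2019; alive 15 Jun 2020; death recorded as 2020.
- Imputed death: 1 Jan 2020, which is 166 days before the alive contact.

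**3. Comparison with 2.7.3.** Take the patient in step 1, but with death reported and no date at all. She is censored at last contact, so her OS time runs to 20 Oct 2020. Adding the correct year moves the end of her OS time back to 10 Feb 2020. The two rules conflict. In addition, 2.7.3 needs a last contact date for a patient known to be dead, and 2.1.9 does not derive one.

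**4. On-treatment window, if the imputed date is used there.** EOT is due 0 to 7 days after last dose, so last dose lies between 3 and 10 Feb 2020. Adding 30 days, the window closes between 4 and 11 Mar 2020. The imputed death of 10 Feb is inside it, while the true death, on or after 20 Oct, is well outside.

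**5. How often, among year-only deaths in the EOT year.** The assumptions, none from the documents, are:
- EOT uniform over the year;
- death after EOT, with exponential survival and median 6 to 30 months;
- an alive contact every 84 days;
- EOT 0 or 7 days after last dose;
- 100,000 deaths per scenario.

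| Quantity | Rule as written | With a floor at last alive contact |
|---|---|---|
| At least one alive contact after the imputed death | 47–57% | 0% |
| Mean days too early | 96–116 | 37–38 |
| More than 30 days after last dose, yet dated on-treatment | 78–87% | 26–36% |

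The floor removes the impossible dates. It does not remove all on-treatment misclassification, because some patients die after day 30 but before the first 12-week contact.

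**6. Effect on the OS hazard ratio.** I simulated 160 patients, 80 per arm, with exponential OS and the BOLERO-2 medians in Protocol 1.1.2 (30.98 and 26.55 months). Censoring at 36 to 54 months was assumed. In 2,000 trials per setting, one, two or three random deaths were moved earlier by the same-year gap between EOT and death (exponential, mean 20 months).
- Mean absolute change in HR: about 0.001 to 0.003; 95th percentile at most 0.007.
- Standard error of log HR: about 0.196.

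**The case against.** The strongest objection is that this may hardly occur. It needs a death date with no month and documented life after the imputed date. Protocol 14.1.4.5.3 asks for complete dates, Protocol 9.4 provides queries for missing values, and regular survival contacts would usually bound the month. The percentages in step 5 are shares of a group that may be empty. This stands as a limit on size. It does not make the rule right for the patients it is written for.

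Three stronger readings are tempting, and the documents do not support them.

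- **The rule creates false on-treatment deaths.** The only call to 5.4.4 is in the secondary-efficacy section. SAP 2.1.8, 2.8 and 2.8.2 do not say whether on-treatment deaths use the recorded or the imputed date. The supportable point is that the SAP leaves this open.
- **Imputed OS is always too short.** Death is itself a reason for treatment to end (Protocol 6.1.5). For a death on treatment, the recorded EOT date may equal or follow the true death. The step 5 simulation places every death after EOT, so its shares lean high.
- **The primary PFS result is distorted.** SAP 2.5.3 does not cite 5.4.4, a patient who progressed by EOT already has her event, and the primary PFS analysis has been reported (cut-off 19 May 2020). This SAP covers the final report.

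The first-of-month branch is also minor: with the month known and kept, the date is at most 30 days early.

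**Conclusion.** The point holds as a defect in a stated rule. Followed literally, 5.4.4 can place a death before a recorded alive contact, and it treats a patient with a known death year worse than 2.7.3 treats one with no death date. That follows from the text without any assumption.

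The size is modest. Few patients should be affected, though their number is not given. The OS hazard ratio would probably move only in the third decimal place, small beside its standard error, and OS is estimated without a formal test. That rests on exponential survival, the assumed censoring window and one to three affected deaths.

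The on-treatment, PFS and ECOG consequences are conditional. They arise only if the imputed date is used in those outputs and, for PFS and ECOG, only in a patient with no earlier event. The on-treatment summary matters most, because one misdated death can be seen there. The change is worth making before the final analysis.

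**What to change.** Rewrite 5.4.4 once, to cover the following.

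1. **Floor.** In every branch, set the imputed death date to the later of the rule date and the last date documented alive, kept within the recorded year or month. Keeping to the recorded month also stops the missing-day, later-year branch from replacing a known month with January.
2. **Source of the floor.** Derive a last-alive date for deceased patients from direct evidence: survival contact reported alive, visits, scans, laboratory samples, vital signs, performance status, doses taken and start of further therapy. Do not apply Table 2-1 unchanged. It includes AE end dates and accepts the EOT date without condition, and either may record the death itself, so the floor could overshoot.
3. **On-treatment deaths.** State in 2.8.2 which death date is used. Do not count a death with an imputed month as on-treatment unless the known dates place it there. The floor alone does not settle this (step 5 of the working).
4. **Protocol.** Reconcile the missing-day branches with the 15th-of-the-month rule in Protocol 14.1.4.5.3, or list the departure in SAP section 4.

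The cost is a short SAP edit, one derived date for deceased patients and the matching code. No new data are needed, since the sources are already collected.
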